Objective: To determine whether 72 weeks of treatment with obeticholic acid compared to treatment with placebo improves nonalcoholic fatty liver disease (NAFLD) as determined from hepatic histology

Treatment groups:

Group 1: Obeticholic acid (25 mg q.d.)

Group 2: Placebo

Type of trial:

Multicenter, double-masked, placebo-controlled, parallel treatment groups with a 72-week histological change as the primary outcome. There will be a planned interim analysis by the trial Data and Safety Monitoring Board (DSMB) after 65 weeks of enrollment, but before any end-of-trial liver biopsies are performed. The interim analysis will commence approximately 65 weeks after the first enrollment using 24 week data from an estimated 25-40% of FLINT trial patients. The interim analysis will focus on (1) emergent safety issues, if any, and (2) differences in the mean changes of serum alanine aminotransferase (ALT) by treatment group that are of sufficient magnitude and direction to warrant the continuation of enrollment and treatment of patients toward the planned sample size and planned follow-up liver biopsies.

Inclusion criteria:

- Age 18 years or older at initial screening interview
- Histological evidence of definite or borderline NASH on a liver biopsy obtained no more than 90 days prior to randomization and a NAFLD activity score (NAS) of 4 or greater with a score of at least 1 in each component of the NAS (steatosis scored 0-3, lobular inflammation scored 0-3, ballooning scored 0-2).

Exclusion criteria:

- Significant alcohol consumption inability to reliably quantify alcohol intake
- Use of drugs historically associated with NAFLD (amiodarone, methotrexate, systemic glucocorticoids, tetracyclines, tamoxifen, estrogens at doses greater than those used for hormone replacement, anabolic steroids, valproic acid, other known hepatotoxins) for more than 2 weeks in the past year prior to randomization Prior or planned bariatric surgery
- Uncontrolled diabetes (HbA1c 9.5% or higher within 60 days prior to enrollment)
- Presence of cirrhosis on liver biopsy
- A platelet count below 100,000 /mm³
- Clinical evidence of hepatic decompensation (serum albumin < 3.2 g/dL, INR >1.3, direct

- bilirubin >1.3 mg/dL, history of esophageal varices, ascites, or hepatic encephalopathy)
- Evidence of other forms of chronic liver disease
- Serum alanine aminotransferase (ALT) greater than 300 U/L
- Serum creatinine of 2.0 mg/dL or greater
- Inability to safely obtain a liver biopsy
- History of biliary diversion
- Known positivity for Human Immunodeficiency Virus infection
- Active, serious medical disease with likely life expectancy less than 5 years
- Active substance abuse including inhaled or injected drugs, in the year prior to screening
- Pregnancy, planned pregnancy, potential for pregnancy and unwillingness to use effective birth control during the trial, breast feeding
- Participation in an IND trial in the 30 days prior to randomization
- Any other condition which, in the opinion of the investigator, would impede compliance or hinder completion of the study
- Failure to give informed consent

Outcome measures

Primary:

Centrally scored histological improvement in NAFLD from baseline to the end of 72 weeks of treatment, where improvement is defined as:

- (1) No worsening in fibrosis; and
- (2) A decrease in NAFLD Activity Score (NAS) of at least 2 points

65 weeks from 1st patient randomized:

Change in serum ALT from baseline to 24 weeks
Adverse events and other safety measures through interim analysis

Secondary changes in the following from baseline to 72 weeks:

NASH diagnosis (from definite or indeterminate NASH to not-NASH)
Fibrosis score
Hepatocellular ballooning score
Each component score in the NAS
Change in serum aminotransferase and gamma-glutamyl transpeptidase (GGT) levels
Change in MRI-determined hepatic fat
Change in fasting markers of insulin resistance (HOMA, adipo-IR index)
Change in post-glucose parameters of insulin (2-hour glucose and fatty acids)
Change in anthropometric measurements (weight, BMI, waist to hip ratio, waist circumference)
Change in bile acid levels
Change in cytokeratin 18 (CK-18) fragment assay
Change in fibroblast growth factor (FGF-19) levels
Change in markers of hepatic apoptosis, inflammation, and fibrosis
Change in health related quality of life (HR-QoL) scores

Screening and enrollment

Up to 16 weeks screening prior to randomization
72-week treatment period
24-week post-treatment washout period
Length of recruitment: 78 weeks (18 months)
Expected enrollment rate: 35 patients each center (~2 patients per month at each center)

Number of clinical centers: 8

Visit schedule:

Screening period can last no more than 16 weeks (112 days) after registration
Randomization: final pre-treatment interview, dispensing of study drug
Follow-up visits: at 2 and 4 weeks and every 12 weeks after randomization throughout the 72-week treatment phase followed by a 96-week visit after 24 weeks of washout period

Randomization: Centrally administered randomization stratified by clinical center, diabetes status, and blocked by calendar time

Statistical analysis: All primary analyses will be on an “intention-to-treat” basis.

The primary analysis is an intention-to-treat analysis in which the proportions of subjects in the active-treatment group (obeticholic acid, 25 mg q.d.) with histological improvement in NAFLD, as defined by the primary outcome measure, is compared with the proportion of subjects in the placebo group in whom there is improvement. The comparison is made with the use of the Mantel–Haenszel chi-square test, stratified according to diabetes status and clinical center. Subjects who do not undergo an end-of-treatment biopsy are classified as not having had improvement.

Vanguard analysis

A formal vanguard analysis, marking the end of the vanguard phase of the FLINT trial, will be performed approximately 65 weeks after the first patient is randomized. The analysis will be focused on interim efficacy outcomes and safety information using data from the estimated 25-40% of patients who will have completed at least 24 weeks of follow-up by the time of the interim analysis. Our pre-specified interim criterion for efficacy for continuing the FLINT trial beyond the vanguard phase is based on serum ALT: the criterion for continuation will be considered met if the upper 95% confidence limit on the between-group mean difference in mean changes from baseline to the 24 week measure of ALT, comparing the obeticholic acid versus placebo groups, is at least a 20% net reduction in serum ALT from the overall baseline mean ALT. The analysis will also include detailed safety data, as required by the DSMB, to determine whether any emergent safety issues are present. This vanguard safety analysis will consist of, but is not limited to, counts of adverse events (AEs) and serious adverse events (SAEs) by treatment group with associated P-values based on Fisher's exact tests or other tests, as appropriate. The final decision as to whether to continue the FLINT trial beyond the vanguard phase will be made by the NIDDK program official for the NASH CRN trial, which will be informed by any recommendations from the FLINT DSMB, taking the interim criterion for efficacy, safety, and other relevant information that may arise into account.

Interim analysis

The DSMB will review one planned interim analysis of the primary histological outcome measure. O'Brien-Fleming statistical stopping guidelines for efficacy will be applied. This interim efficacy analysis will occur when approximately 50% (140 of the 280 patients) have completed both baseline and 72 week biopsies. Based on the Lan-DeMets method for group sequential trials using O'Brien-Fleming boundaries (Reboussin et al., 2000), the levels of significance for the interim and final analyses will be $\alpha=0.00305$ and $\alpha=0.049$, respectively.

Sample size considerations

- Total of 280 patients in 2 groups of equal size (140 per group)
- Primary comparison: Obeticholic acid group vs. Placebo group
- Primary outcome measure: Histological improvement in NAFLD (defined above)
- Error protection: Type I = 0.05 and Type II = 0.10 (90% power)
- Missing data: 10% will not have 72 week biopsies and will be considered not improved
- Minimum clinically important difference:
 - 50% higher relative rate of improvement in the obeticholic acid group vs. the placebo group
- Assumed response rates:
 - Expected percent with improved NAFLD (defined above) in the placebo group: 39% (based on PIVENS data and 2 to 1 split for patients on vs not on vitamin E at start of trial)
 - Expected percent with improved NAFLD in the obeticholic acid group: 58%

Safety monitoring: NIDDK appointed DSMB will monitor the data for safety and efficacy for outcomes such as hepatotoxicity, pregnancy, and any other outcomes or events identified as safety-related.

1. Hypothesis and principal objective

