3.2 Treatment groups

Patients who have signed an informed consent statement and who meet the eligibility criteria will be randomly assigned to one of the two groups for 72 weeks of treatment:

Group 1: Obeticholic acid (25 mg daily as a capsule orally)

Group 2: Placebo (as an identical capsule as active drug)

The randomization scheme will assign patients in randomly permuted blocks of assignments stratified by presence of diabetes and clinical center; block size will be determined randomly. This scheme will ensure that the two groups will be balanced by calendar time of enrollment (to minimize secular effects), by clinic (to minimize clinic-specific effects of differences in patient populations and management), and by diabetes status.

The randomization plan will be prepared and administered centrally by the Data Coordinating Center (DCC) but will not require real time interaction with a DCC staff member. Requests for randomizations will be made by the clinics using a web-based application. An assignment will be issued only if the database shows that the patient is eligible, has signed the consent statement, and has had all required baseline data keyed into the database.

Drug administration

Obeticholic acid will be administered orally as a single capsule of 25 mg per day. An identical appearing placebo capsule will be taken daily by patients assigned to the placebo group. Patients will be instructed to take the medication at the same time each day to the extent that is practical, and they will be told not to take more than one dose in a day if they miss a dose.

Rationale for 25 mg daily dose of obeticholic acid

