3.4 Primary endpoint

Liver histology improvement will be the basis of the primary end point. The definition of improvement after treatment as the primary outcome measure requires the following two conditions:

- No worsening of the fibrosis score and
- A decrease in NAS by 2 or more points

Justification for performing a liver biopsy

NASH is a clinico-pathologic entity and liver biopsy characteristics are required for diagnosis of NASH. Currently, there are no non-invasive markers to diagnose or grade NASH. Therefore, a liver biopsy is needed to document improvement in NASH. Several of the histologic features of NASH including ballooning degeneration and fibrosis have prognostic significance and predict liver-related deaths in patients with NAFLD. Therefore, documentation of improvement of the pathologic lesions of NASH in liver biopsy is needed to show efficacy in a clinical trial.

Rationale for using the Nonalcoholic Fatty Liver Disease Activity Score (NAS)

The primary outcome measure requires improvement in NASH activity after 72 weeks of treatment as determined by liver biopsies pre- and post-treatment. The measure is derived from changes from baseline to the end of treatment in the NASH CRN NAFLD activity score (NAS).⁷⁹ The NAS ranges from 0 to 8 (highest activity) and is calculated as the unweighted sum of three components of the standardized histologic feature scoring system for liver biopsies:

$$\begin{aligned} \text{NAS} = & \text{Steatosis score (0-3)} \\ & + \text{Lobular inflammation score (0-3)} \\ & + \text{Hepatocyte ballooning score (0-2)} \end{aligned}$$

The NAS provides a semi-quantitative tool to assess treatment response in a clinical trial. It has been validated, and this instrument is considered a gold standard in the field. It was utilized to assess the efficacy in the PIVENS and TONIC trials conducted by the NASH CRN.³⁷ This would also provide a tool to compare the findings across various treatment trials within and outside the NASH CRN. Therefore, we believe that the NAS provides the most objective and reproducible tool that is available to assess efficacy of treatment in NASH.

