7.1 Hypotheses and outcome measures

Primary Hypothesis

Obeticholic acid at 25 mg orally once daily for 72 weeks is better than placebo in improving liver histologic parameters as measured by the NAFLD activity score in patients with biopsy evidence of nonalcoholic steatohepatitis.

The ***primary outcome measure*** requires the following two conditions:

- No worsening of the fibrosis score
- A decrease in NAS by 2 or more points

Secondary Hypotheses

- Administration of the farnesoid X receptor ligand obeticholic acid for 72 weeks to subjects with biopsy evidence of nonalcoholic steatohepatitis will result in improvement in insulin sensitivity as measured by HOMA-IR and the adipo-IR index.
- Administration of the farnesoid X receptor ligand obeticholic acid for 72 weeks to subjects with biopsy evidence of nonalcoholic steatohepatitis will result in reduction in MRI-determined hepatic fraction.
- Administration of the farnesoid X receptor ligand obeticholic acid for 72 weeks to subjects with biopsy evidence of nonalcoholic steatohepatitis will result in a greater decrease in the proportion of patients with a biopsy diagnosis of definite or probable NASH compared to placebo
- Administration of the farnesoid X receptor ligand obeticholic acid for 72 weeks to subjects with biopsy evidence of nonalcoholic steatohepatitis will result in reduction in serum aminotransferase and gamma-glutamyl transpeptidase.

Secondary outcome measures

- Change in histological diagnosis from NASH or indeterminate for NASH to not-NASH
 - Whereas the primary endpoint is based on changes of specific features of NASH as summed in the NAS, it does not actually evaluate whether NASH resolves with treatment. Thus this essential secondary endpoint of determining whether NASH resolves with treatment will be a major outcome of the trial.
 - It will be anticipated that some subjects judged to have NASH on their locally read entry biopsy will not have NASH on central reading of deeper cuts from the same block.
 - For the purposes of this analysis, subjects with borderline NASH will be included with subjects with definite NASH.
- Mean changes in NAS
- Changes in individual histological characteristics:
 - Mean fibrosis score
 - Change from stage 1b to 1a fibrosis
 - Steatosis
 - Lobular inflammation
 - Portal chronic inflammation
 - Ballooning
 - Other specific features from the histologic scoring system
- Changes in serum aminotransferase levels:
 - Mean change in ALT, AST, and GGT

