7.2 Statistical analysis

Primary hypothesis

Statistical analyses for the primary hypothesis will follow the intention-to-treat paradigm, which means that all randomized patients with baseline and 72 week liver biopsies will be included in the treatment group to which they were assigned. Any randomized patient who does not have the requisite biopsies will be accounted for and compared by assigned treatment group. Patients not able to be included in the intention-to-treat analyses will be compared to those who are included with respect to demographic and other characteristics.

Since the primary outcome measure, defined in sections 3.4 and 6.1, is a binary indicator of improvement in histologic activity score after 72 weeks of treatment compared to baseline and since the randomization is stratified by clinic and diabetes status, P-values will be derived from the Mantel-Haenszel χ^2 test for stratified 2x2 tables. The proportion of patients improved in the group assigned to obeticholic acid will be compared to the group assigned to placebo and a two-tailed p-value of ≤ 0.05 will be considered statistically significant.

Stratification

Given the randomized design and adequate size planned for the FLINT trial, it is unlikely that confounding of the treatment groups by covariates related to the change in histologic activity score will occur. However, if confounding should occur, multivariate-adjusted logistic regression analyses with histologic improvement as the binary response and treatment group indicator and any suspected confounders as covariates will be carried out to determine the sensitivity of the primary P-value to confounding.

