7.5 Vanguard analysis

An unmasked vanguard analysis, using change in ALT (U/L) from baseline to the 24 week follow-up visit as the primary vanguard outcome, will be carried out for review by the DSMB in order to advise the NIDDK on whether the FLINT trial should continue. The vanguard design requires that the vanguard analysis and the decision to continue must be completed before any patient undergoes a 72 week end-of-study biopsy. This means that the vanguard analysis of ALT change must occur approximately 65 weeks after the first randomized patient is enrolled when between 70 (25% of total sample size) and 112 (40%) will have a 24 week ALT measure, but before the first patient (or any other patient) has undergone a 72 week liver biopsy.

The vanguard analysis statistical guideline indicating sufficient evidence that, compared to placebo, 24 weeks of treatment with obeticholic acid results in a greater reduction in ALT (BL – 24 weeks) will be considered met if the upper 95% confidence limit for the net percentage reduction in mean ALT (BL-24 weeks) in the obeticholic acid group vs. placebo group is greater than or equal to 20%. The net reduction and 95% upper confidence interval will be calculated from a multiple linear regression model with patient level changes in ALT (U/L) at baseline minus ALT (U/L) at 24 weeks as the response variable (y) and independent variables: obeticholic acid indicator ($x_1=1$, if obeticholic acid, 0, if placebo) and baseline ALT (U/L) (x_2): $E(y_i)=\beta_0+ \beta_1x_1+ \beta_2x_2+\epsilon_i$, $i=1,2,\dots,n$; n =number of patients in the vanguard analysis and ϵ_i are i.i.d. Gaussian($0,\sigma^2$).

The estimated between group (obeticholic acid vs. placebo) difference in mean change in ALT from BL

to 24 weeks is b_2 with 95% CI: $b_2 \pm t_{n-3} \widehat{\sigma}(b_2)$ where t_{n-3} is the 97.5th percentile of the t-distribution with $n-3$ degrees of freedom and $\widehat{\sigma}(b_2)$ is the estimated standard error of b_2 from the regression analysis. The estimated net reduction in ALT in the obeticholic acid group, expressed as percentage of the overall baseline mean ALT, \overline{ALT} , is $100 \times b_2 / \overline{ALT}$ with upper 95% confidence limit: $100 \times [b_2 + t_{n-3} \widehat{\sigma}(b_2)] / \overline{ALT}$. SAS PROC REG will be used to fit the regression model and calculate the upper 95% confidence limit to determine whether its value is a 20% or more net reduction in ALT.

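### The primary Mantel-Haenszel test is valid but leaves out baseline NAS; naming it in advance as a covariate would cost almost nothing and could add about 0 to 5 points of power

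*Protocol*

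**What the plan says.** - **Primary test.** The synopsis (Statistical analysis) specifies a Mantel-Haenszel "chi-square test, stratified according to diabetes status and clinical center". Section 7.2 repeats the test and gives its reason: "since the randomization is stratified by clinic and diabetes status". Section 3.2 confirms the allocation: "randomly permuted blocks of assignments stratified by presence of diabetes and clinical center". The synopsis also states "Number of clinical centers: 8", so there are 8 × 2 = 16 strata, or 280/16 = 17.5 patients per stratum on average.
- **Outcome.** The synopsis requires no worsening of fibrosis together with "A decrease in NAFLD Activity Score (NAS) of at least 2 points", scored centrally. Section 3.4 agrees: "A decrease in NAS by 2 or more points".
- **Baseline NAS.** Sections 4.2 and 5.2 require a qualifying biopsy within 90 days before randomization, with NAS of at least 4 and at least 1 in each component. Section 3.4 gives the scale as 0 to 8.
- **Adjustment.** Section 7.2 plans an adjusted logistic regression only if confounding should occur. Its purpose is to test how sensitive the primary P-value is. The covariates are whatever is suspected at the time, and baseline NAS is not named.
- **Missing biopsies.** The synopsis and section 7.3 class patients without a week-72 biopsy as not improved.

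**The concern.** The outcome is a change from baseline cut at 2 points, so the baseline score enters the definition of response. Response would be unrelated to baseline only if follow-up NAS rose by a full point for each baseline point. Two features of the plan make a weaker link likely. Entry selects on NAS of at least 4, and section 5.10 (Placebo) attributes part of the improvement seen on placebo to sampling variability. Both point to regression to the mean, so patients with higher scores should respond more often.

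If so, variation in response that could be explained stays unexplained in the primary test. A chance imbalance in baseline NAS would also carry into the primary estimate. Section 7.2 would deal with such an imbalance only after someone had decided that confounding was present and chosen the covariates. At stake is some power and some freedom from after-the-fact choice. The validity of the test is not at stake.

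**Working it through.** **1. The plan's own figure.** Inputs from the synopsis and section 7.4: 39% v 58%, 140 per group, two-sided 0.05, 90% power. The placebo rate is (2/3)(48%) + (1/3)(20%) = 38.67%, rounded to 39%.

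Power = Φ{[|p2 − p1|√n − 1.96√(2p̄(1 − p̄))] / √[p1(1 − p1) + p2(1 − p2)]}, with p̄ = 0.485:

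- numerator: 0.19 × 11.832 − 1.96 × 0.7068 = 2.248 − 1.385 = 0.863
- denominator: √(0.2379 + 0.2436) = 0.694
- Φ(0.863/0.694) = Φ(1.243) = 0.893

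The exact requirement at 39% is 144 per group. With 38.67%, it is 139 per group and power is 0.903. The stated 280 and 90% therefore reproduce without any use of baseline NAS, taking 39% and 58% as the final intention-to-treat rates.

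**2. How strong could the association be?** The protocol gives neither the NAS distribution nor its link with response, so both must be assumed. Take NAS 4 to 8 with mean 5.5 and SD 1.2, 39% response, and residual SD 1.3 to 1.7. The correlation ρ between baseline NAS and response then depends on the slope of follow-up NAS on baseline:

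| Slope | ρ |
|---|---|
| 0.2 | 0.41–0.51 |
| 0.4 | 0.32–0.41 |
| 0.6 | 0.22–0.28 |
| 0.8 | 0.11–0.15 |
| 1.0 | 0 |

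The fibrosis condition was not modelled and could lower these values. Counting 10% as failures lowers each by about 8%.

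**3. Approximate gain.** Adjustment acts roughly as if n were 140/(1 − ρ²). At 39% v 58%:

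| ρ | Effective n per group | Power |
|---|---|---|
| 0 | 140 | 0.893 |
| 0.2 | 145.8 | 0.905 |
| 0.3 | 153.8 | 0.919 |
| 0.4 | 166.7 | 0.938 |
| 0.5 | 186.7 | 0.959 |

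**4. Simulation.** Setting: 280 patients, 16 center-by-diabetes strata, 39% v 58%, 3,000 trials per case (Monte Carlo standard error about 0.6 point). Two NAS distributions over 4, 5, 6, 7, 8 were assumed: 25/28/22/17/8% and 40/30/18/9/3%. Center and diabetes had no effect on response. The ranges cover the two distributions.

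| Odds ratio per NAS point | Planned Mantel-Haenszel | Logistic, treatment + NAS |
|---|---|---|
| 1.0 | 0.89 | 0.89 |
| 1.3 | 0.89–0.90 | 0.90–0.91 |
| 1.6 | 0.89 | 0.91–0.92 |
| 2.0 | 0.90–0.91 | 0.93–0.94 |

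That is a gain of about 0 to 3 points. A separate simulation of the standardized risk difference from a model with treatment, diabetes, 8 centers and NAS kept type I error near 5%. It lost no power when there was no association, and gained about 1 to 5 points at odds ratios of 1.3 to 2.0. Together the range is about 0 to 5 points.

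**5. Baseline NAS as extra strata.** Splitting NAS at 6 gives 32 strata and changes power by about −2 to +1 points. Using each level from 4 to 8 gives 80 strata of 280/80 = 3.5 patients and loses about 2 to 10 points. About 32 to 37 of the 280 patients then fall in strata containing one group only and contribute nothing.

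**The case against.** The strongest reply is that nothing here is wrong. The strata follow the randomization, section 7.2 says so, the stated power does not depend on baseline NAS, and naming covariates is often left to an analysis plan that is not shown. All of that stands as a defence of validity. It does not fully answer the point, because the protocol itself fixes the primary test without baseline NAS and makes any adjustment conditional on confounding being found.

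A reader might infer more than the documents support, in four ways:

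- **That a low baseline score mechanically prevents a 2-point fall.** It does not. The lowest eligible NAS is 4 and the floor is 0, so every eligible patient has at least 4 points of room. Section 7.1 does expect that "some subjects judged to have NASH on their locally read entry biopsy will not have NASH on central reading", but this concerns the diagnosis of NASH and gives no NAS values. A central score of 2 or 3 would still permit response. Only 0 or 1 would not, and the documents indicate no such cases.
- **That no reason is given for the strata.** Section 7.2 gives one.
- **That the vanguard model in section 7.5, which adjusts ALT change for baseline ALT, contradicts the primary analysis.** One outcome is continuous and the other binary, and different methods are legitimate. The vanguard model shows only that the authors accept baseline adjustment in principle.
- **That the gain is large.** The approximation reaches 5 points only at about ρ = 0.43. An odds ratio of 2.5 per NAS point corresponds to ρ of about 0.44, and 3 to about 0.49. From NAS 4 to NAS 8 these compound to 2.5⁴ ≈ 39 and 3⁴ = 81, and nothing in the documents supports such gradients.

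**Conclusion.** The point holds as a low-cost improvement. The planned test is sound and supports the stated power, but it leaves unused a baseline value that the outcome itself requires and that is probably prognostic. The gain is about 0 to 5 points of power for odds ratios of 1.0 to 2.0 per NAS point, and larger only if the association is stronger. The range rests on an assumed NAS distribution and an assumed association, since the documents give neither. It also takes 39% and 58% as final rates. If 10% of patients are failures for lack of a biopsy, unrelated to baseline NAS, the association is diluted by roughly a tenth and the gain shrinks somewhat. A second, smaller benefit is that a named covariate replaces the open-ended choice in section 7.2.

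**What to change.** Before unmasking, and so before the interim look at histology in section 7.6:

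- Define the primary comparison as a covariate-adjusted risk difference standardized from a logistic model with treatment, diabetes, center and centrally read baseline NAS.
- Enter NAS as a covariate and not as additional Mantel-Haenszel strata.
- Keep all randomized patients in the analysis, with those lacking a week-72 biopsy classed as not improved. Their baseline biopsies therefore also need a central reading.
- Keep the planned Mantel-Haenszel test as a sensitivity analysis.

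If the sponsor prefers to leave the Mantel-Haenszel test primary, naming the adjusted model as a fixed supportive analysis would still remove the discretion in section 7.2, though the primary test would not gain power.

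The cost is a change of wording and one model, with no new visits or procedures. The downside is a slightly less simple analysis, with little return if baseline NAS proves only weakly related to response.
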